# 3.1.3 Allocation to Interventional Group

Participants will be randomized to one of three locations: nasofacial sulcus, lateral forehead, or upper back. Additionally, subjects will be randomized to receive the intervention with vibration anesthesia device on their first (left) or second (right)-sided injection. This is a split body study so each participant will receive 2 total injections – one with and one without the intervention. Randomization will be achieved by the selection of a sealed envelope by each study participant, that will have a location and an order listed. This will randomize subjects and will ensure that groups can be balanced, by creating equal numbers of envelopes for each of the groups.

### 3.2 Study Endpoints

### 3.2.1 Primary Study Endpoints

Each injection will be evaluated by 100mm visual analog scale (VAS) for acute pain immediately after the injection is complete. Patients visually indicate by drawing on paper where their pain is on a 10 cm line, with one end labelled no pain at all and the other worst pain imaginable. The primary endpoint is a statistically significant mean reduction in acute pain on VAS of 10mm or more, per Bijur et al, who determined that this change indicates a real clinical change in acute pain.

#### 3.2.2 Secondary Study Endpoints

Following the completion of both injections, volunteers will indicate which injection they preferred, with a no preference option included. Patients will also be queried on demographic information after the injections have been completed. They will be asked age, sex, and role at the University of Pennsylvania. Because pain is characterized as quantitative AND qualitative, there will be a free response section for comments, specifically asking "Do you have any comments on how the kinetic anesthesia device affected your injection experience?" A second qualitative entry section will ask: "Were you bothered in any way by the KAD [check yes or no] if so please comment"

#### 4 Study Population and Duration of Participation

#### 4.1 Inclusion / Exclusion Criteria

Inclusion / Exclusion Criteria will be verified by the Principal Investigator.

#### 4.2 Key inclusion criteria

- 1. Adult volunteers greater than or equal to 18 years of age
- 2. Able and willing to provide informed consent
- 3. Able to comprehend and comply with study instructions, and able to complete necessary evaluations.

# 4.3 Exclusion Criteria

- 1. Patients unable or unwilling to provide informed consent.
- 2. Patients with lidocaine allergy
- 3. Patients with known pain-related or neurological condition.
- 4. Patients with a known cardiac condition

- 5. Patients taking medications with a known Clinically Significant Drug Interaction with lidocaine.
- 6. Patients who are pregnant or Nursing mothers.
- 7. Vulnerable populations

### 4.4 Subject Recruitment

Subject recruitment will occur by email to the Perelman School of Medicine student body. Email text is attached. Further recruitment will occur from flyers posted around the University of Pennsylvania campus and University City area. Flyer attached. Study recruitment information will be circulated via the UPHS broadcast email. Materials attached. The study will be posted on the iConnect tool.

# 4.5 Duration of Study Participation

Recruitment and enrollment period: 2 months

Subjects' length of participation in the study: 1 day.

The entire encounter should take less than one hour.

Project date of the proposed study: Recruitment and enrollment will commence with IRB approval. A total time of 6 months is requested for data analysis.

### 4.6 Total Number of Subjects and Sites

50 subjects enrolled for the study taking place at one site – Perelman Center for Advanced Medicine.

### 4.7 Vulnerable Populations:

Vulnerable populations will not be included in this study

### 5 Study Intervention (Study drug, device, biologic, vaccine, food etc.)

#### 5.1 Description

Blaine Labs Vibration Anesthesia Device. The device will be used as directed by the manufacturer, in the following manner: The device will be held by the person giving the injection in their off hand. It will be firmly pressed on the skin, turned on, adjacent to the injection 1-2 seconds before the injection is given. The injection will be given into the lighted target area of the kinetic anesthesia device. The device will be removed 1-2 seconds after the needle is withdrawn.

This device is on the US market legally. This is a class 1 device, exempt from the need for approval or clearance. Per the Code of Federal Regulations

(https://www.accessdata.fda.gov/scripts/cdrh/cfdocs/cfCFR/CFRsearch.cfm?FR=890.5975-) this device may be used in clinical care or research.

The device is being used in this research study in accordance with the FDA description

Further information regarding the device is attached in HS-ERA.

#### 5.2 Receipt

The device will be purchased directly from Blaine Labs and shipped to [name] in the Perelman Center for Advanced Medicine.

#### 6 Study Procedures

### 6.1 Study Intervention Phase

1. The study will take place in an examination room in the Dermatologic Surgery clinic at the Perelman Center for Advanced Medicine.

2. The KAD used will be the Blaine Labs Vibration Anesthesia Device. The device will be purchased from Blaine Labs directly.

3. Injections will be made up of 0.5mL of room temperature 1% lidocaine buffered with 8.4% sodium bicarbonate, procured from the dermatologic surgery clinic. Injections will use the standard syringe with 30-gauge needle.

4. Before any procedure is done or information is collected for the study, subjects will be asked to read and sign the consent form. Adequate time will be given for subjects to review the Informed Consent Document and review any of their questions or concerns with the study staff or Principal Investigator.

5. Baseline vital signs (heart rate, blood pressure,) will be obtained prior to the first injection. The participant's baseline respiratory rate and adequacy of ventilation will also be noted. We will additionally specify that the study procedure will take place in a setting where resuscitative equipment and personnel for treating adverse reactions will be immediately available."

6. Then each subject will be randomized to one location: nasofacial sulcus, lateral forehead or lateral back.

7. Each subject will be randomized to receive the intervention with KAD either first or second.

8. The first injection will always be on the left side and the second will always be on the right

9. When the KAD is used for the injection, it will be held by the person giving the injection in their off hand. It will be firmly pressed on the skin, turned on, adjacent to the injection 1-2 seconds before the injection is given. The injection will be given into the lighted target area of the KAD. The device will be removed 1-2 seconds after the needle is withdrawn.

10. Each injection will be given in accordance with the current standard of practice. Injections will be given using the formulation and needle noted above. Injections will be given with the needle held perpendicular to the skin. The speed of the injection will be slow, aiming for 5 seconds to empty the syringe. All injections will be performed by [name], with verbal cues standardized.

11. After each injection, study participants will be asked to document their level of acute pain using the VAS. A paper and pen version of the scale will be used.

12. After both injections are complete, safety vitals will again be obtained (heart rate, blood pressure, respiratory rate and adequacy of ventilation) in order to assess whether subject has tolerated the injection without any adverse reactions. If necessary, repeat vitals will be obtained until the Principal Investigator feels the subject is medically clear to leave.

13. After both injections are complete the study participant will be asked to fill out the short questionnaire about preference of injection, qualitative comments, age, and sex.

14. The location and order of the injections will be noted by study personnel. The VAS scales will be measured.

15. At this point, data collection will be complete. Unless an adverse event was noted, or subject has additional questions or concerns regarding their participation or study-related procedures, participants will be compensated and will be free to go at this point.

16. The kinetic anesthesia device will be cleaned with an alcohol swab. Study personnel will wash hands and repeat the exercise on the next participant.

# 6.2 Subject Withdrawal

Subjects may withdraw at any time by indicating this to investigators.

#### 7 Study Evaluations and Measurements

Each injection will be evaluated by 100mm visual analog scale (VAS) for acute pain immediately after the injection is complete. Patients visually indicate by drawing on paper where their pain is on a 10 cm line, with one end labelled no pain at all and the other worst pain imaginable. The primary endpoint is a statistically significant mean reduction in acute pain on VAS of 10mm or more, per Bijur et al, who determined that this change indicates a real clinical change in acute pain. Following the completion of both injections, volunteers will indicate which injection they preferred, with a no preference option included. Patients will also be queried on demographic information after the injections have been

completed. They will be asked age, sex, role at University of Pennsylvania. Because pain is characterized as quantitative AND qualitative, include a free response section for comments, specifically asking Do you have any comments on how the kinetic anesthesia device affected your injection experience? A second qualitative entry section will ask: Were you bothered in any way by the VAD [check yes or no] if so please comment

# 7.1 Vital Signs

Vital signs will be collected by the study staff overseeing the visit. Baseline vitals will be established prior to the first injection and recorded on the data source sheet. Post-Injection Vitals will be obtained following the second injection, before subjects begin to fill out their final survey sheet. If necessary, repeat vitals will be obtained until the Principal Investigator feels that the subject is medically cleared to leave.

# 8 Statistical Plan

# 8.1 Primary Endpoint

Each injection will be evaluated by 100mm visual analog scale (VAS) for acute pain immediately after the injection is complete. Patients visually indicate by drawing on paper where their pain is on a 10 cm line, with one end labeled no pain at all and the other worst pain imaginable. The primary endpoint is a statistically significant mean reduction in acute pain on VAS of 10mm or more, per Bijur et al, who determined that this change indicates a real clinical change in acute pain. Quantitative VAS data will be analyzed by a two-tailed t-test, and by linear regression model, incorporating location, and order of intervention (i.e. intervention

first or second).

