#### 1.1 Background and Relevant Literature

In many dermatologic procedures performed with local anesthetic, the injection of anesthetic is the most painful part of the procedure, and is thus one of the greatest barriers to complete comfort and enhanced patient satisfaction. Methods to minimize injection pain have been proposed and include slow rate of injection, with warmed, buffered lidocaine to decrease discomfort of local anesthetic injection (Kuboa), Vibrating devices have been shown to reduce the pain of local botulinum toxin injections, steroid injections for keloid treatment, local anesthetic injections in eyelid surgery, and in venipuncture in a pediatric emergency department. It is thought that vibration decreases the pain of injection by the gate control theory of pain, first proposed by Melzack and Wall, which asserts that the vibrating neural input overrides painful signals and prevents them from reaching the central nervous system. No study has yet investigated vibration devices for lidocaine injection at multiple body sites in the dermatologic surgery setting. The VAS is reported to be the most frequently used assessment instrument to evaluate the analgesic effects of various therapies and can detect minute pain changes. It has been systematically evaluated by Bijur et al, who determined that a change of 10mm or more on this scale represents a real clinical change in acute pain.

Kuboa et al. Guidelines for the use of local anesthesia in office-based dermatologic surgery. JAAD. 2016;74:6:1201-1219 Sharma P, et al. Investigating the efficacy of vibration anesthesia to reduce pain from cosmetic botulinum toxin injections. Aesthet Surg J.

2011;31:966-971 Park KY, Kim BJ et al. Vibration Anesthesia for Pain Reduction During Intralesional Steroid Injection for Keloid Treatment. Derm Surg. 2017;43:724-727. Fayers, T et al. Vibration-assisted anesthesia in eyelid surgery. Othalmology. 2010;117:1453-1457 Baxter AL et al. An integration of vibration and cold relieves venipuncture pain in a pediatric emergency department. Pediatr Emerg Care.

2011;27:1151-1156 KC Smith, JC Liu et al. Vibration anesthesia: A noninvasive method of reducing discomfort prior to dermatologic procedures. Dermatology Online Journal. 2004;10(2):1 Reed Michael D, van Nostran W. Assessing pain intensity with the visual analog scale: a plea for unity. J Clinic Pharm. 2014; 54:241-244. Bijur PE, Silver W, Gallagher EJ. Reliabil15.

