# 2.1 Primary Objective

To determine the effect of KAD versus no device on pain of lidocaine injection, participants will be asked to evaluate each injection on a 100mm visual analog scale (VAS). Ratings will be quantified at intervals of 1mm from 1mm to 100mm, with 1 mm representing "no pain at all" and 100 mm representing "worst pain imaginable." VAS ratings from injections with and without the device will be compared in each patient.

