# 8.3 Sample Size and Power Determination

Sample size was calculated in STATA using the change in VAS needed for clinical significance, in concordance with effect sizes and standard deviations from previous studies. Sample size calculated to detect a clinically significant difference at each of three locations with alpha = 0.05 and a power of 0.8.

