# 8.4 Statistical Methods

Quantitative VAS data will be analyzed by a two-tailed t-test, and by linear regression model, incorporating location, and order of intervention (i.e. intervention first or second). Quantitative preferential data will be analyzed by logistic regression model incorporating location and order of intervention.

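### Read literally, the primary endpoint (significant and a mean reduction of at least 10 mm) has power of at most about 0.50 at a true 10 mm, so the 0.8 in Section 8.3 must describe another criterion or a larger effect

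*Combined protocol and SAP*

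**What the plan says.** Sections 3.2.1, 7 and 8.1 all define the primary endpoint in the same sentence: "The primary endpoint is a statistically significant mean reduction in acute pain on VAS of 10mm or more". The 10 mm comes from Section 1.1, which reports from a cited study that "a change of 10mm or more on this scale represents a real clinical change in acute pain".

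The comparison is within person. Section 2.1 says "VAS ratings from injections with and without the device will be compared in each patient".

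The analysis in Section 8.4, also given in 8.1, is: "Quantitative VAS data will be analyzed by a two-tailed t-test, and by linear regression model". The regression includes location and order. Neither section gives a null value other than zero or says how the 10 mm condition is to be applied.

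Section 8.3 says the sample size was calculated "using the change in VAS needed for clinical significance, in concordance with effect sizes and standard deviations from previous studies", and then: "Sample size calculated to detect a clinically significant difference at each of three locations with alpha = 0.05 and a power of 0.8". It prints no effect size, SD or number per location. Section 4.6 gives the total: "50 subjects enrolled for the study taking place at one site". Section 3.1.3 plans equal numbers of envelopes per group, so 50/3 gives 16 or 17 participants per location.

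**The concern.** The endpoint sentence sets two hurdles: a significant result, and an observed mean reduction of 10 mm or more. The named test has only the first. The power statement in 8.3 does not say which of the two it describes.

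The natural reading of 8.3 is that the clinically significant change it was sized for is the 10 mm of Section 1.1. That is an inference, because 8.3 prints no figure. If it is right, the power statement and the endpoint sentence cannot both refer to the same success rule. A device that delivers exactly the benefit the protocol calls clinically real would miss the endpoint as written about half the time or more.

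The two criteria also disagree over a plausible range of results. In an open-label trial with no stated order of precedence between them, success could be declared on whichever suits the data.

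**Working it through.** **Inputs from the protocol.** Threshold 10 mm (1.1, 8.1); two-sided alpha 0.05 and power 0.8 (8.3, 8.4); 50 participants (4.6), so 16 or 17 per location; paired differences (2.1).

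**Assumption.** No SD is printed, so the SD of the paired differences has to be assumed. The main values used are 13.6 mm and 20 mm.

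**Step 1: can the 0.8 be reproduced?** Not directly, because effect and SD are both missing. Solving backwards, a paired t-test against zero at a true 10 mm has power 0.80 when the SD of differences is:

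- 13.34 mm for n = 16
- 13.81 mm for n = 17
- 24.74 mm for n = 50

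The value 13.6 mm lies between the first two. It is therefore roughly the SD at which the printed per-location 0.8 would be right for significance alone. It is not an estimate from data.

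**Step 2: the ceiling, which needs no SD.** For any n, SD and alpha,

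P(significant and mean ≥ 10) ≤ P(mean ≥ 10).

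If the true mean is 10 mm and the sample mean is distributed symmetrically around it, the right-hand side is 0.50. This holds per location and pooled. Skewed VAS differences could move it slightly, hence *about* 0.50.

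**Step 3: size under assumed SDs, true reduction 10 mm.** Significance alone is P(t > t_0.975,n−1) under the noncentral t. The joint rule is P(mean ≥ max(10, t_0.975,n−1 · s/√n)), integrated over the chi-square distribution of s².

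| n | SD (mm) | Significance alone | Joint rule |
|---|---|---|---|
| 16 | 13.6 | 0.785 | 0.499 |
| 17 | 13.6 | 0.812 | 0.500 |
| 16 | 20 | 0.465 | 0.423 |
| 17 | 20 | 0.491 | 0.439 |
| 50 | 13.6 | 0.999 | 0.500 |
| 50 | 20 | 0.934 | 0.500 |
| 50 | 25 | 0.792 | 0.500 |

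Simulation with 200,000 draws agrees: 0.813/0.499 for n = 17, SD 13.6, and 0.934/0.501 for n = 50, SD 20.

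**Step 4: true reduction at which the joint rule reaches 0.80.** Where the 10 mm bar is the binding condition, this is 10 + 0.8416 · SD/√n:

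- n = 17, SD 13.6: 10 + 0.8416 × 13.6/√17 = 12.78 mm
- n = 50, SD 13.6: 10 + 0.8416 × 13.6/√50 = 11.62 mm
- n = 50, SD 20: 10 + 0.8416 × 20/√50 = 12.38 mm

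For n = 17, SD 20, significance also binds, and the full integration gives 14.97 mm.

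**Step 5: where the two criteria disagree at n = 50.** The smallest significant observed mean is t_0.975,49 · s/√50, with t = 2.010:

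- s = 13.6: 2.010 × 13.6/7.071 = 3.87 mm
- s = 20: 2.010 × 20/7.071 = 5.68 mm

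Any observed mean from that value up to 10 mm passes the t-test and fails the endpoint sentence.

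**The case against.** The strongest reply is that no printed figure has been shown to be wrong. Section 8.3 speaks of detecting a clinically significant difference, which is the usual description of a test against zero powered at the relevant effect, and 8.1 and 8.4 name only such a test. On that reading 10 mm is the design effect and 0.8 can hold. Section 8.3 also refers to effect sizes from previous studies, so a planning effect above 10 mm cannot be ruled out. Both points stand, and they are the only two ways to reconcile the 0.8 with the endpoint. But the first makes the endpoint sentence wrong in three places, the second requires 8.3 to print the effect, and no section settles which applies.

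The 0.50 ceiling is also generic: any rule that requires the observed mean to reach the true mean passes about half the time. That is so. What is specific to this trial is that such a rule is printed as the primary endpoint beside a power of 0.8 and a test without the rule.

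The SD of 13.6 mm is chosen, and the per-location fall from about 0.8 to 0.5 depends on it. With a larger SD the loss is small (0.465 to 0.423 at n = 16, SD 20) because power is already low. This limits the illustrations but leaves the ceiling untouched.

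Finally, naming one pooled paired t-test as decisive goes further than removing the ambiguity. That is fair. It follows Section 2.1, which compares within patients and not by location, but it is a choice the sponsor must make.

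**Conclusion.** The concern holds. As written, the primary success rule has power of at most about 0.50 if the true reduction is 10 mm, at any sample size or SD, per location or pooled. This rests on the literal reading of the endpoint sentence and on approximate symmetry of the sample mean; no missing input is needed.

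It does not show that the 0.8 was miscalculated. It shows that the 0.8 cannot describe the printed endpoint at 10 mm, and that the protocol leaves open which criterion or effect it does describe. In addition, 8.3 gives power only per location, and none is printed for the overall comparison that is the primary objective. The figures for particular SDs are sensitivity values, since the protocol prints no SD.

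**What to change.** **Preferred.** Replace the endpoint sentence in 3.2.1, 7 and 8.1 with text such as:

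> The primary endpoint is the within-participant VAS difference in mm (no device minus KAD). The mean difference over all participants will be tested against zero with a two-sided paired t-test at alpha 0.05. The mean and its 95% CI will be interpreted against 10 mm; 10 mm is not part of the test.

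The regression with location and order can stay. In 8.3, say that the 0.8 is the power of this test, and give the true difference, the SD of paired differences and the n to which it refers, per location or pooled.

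**Alternative.** Keep the 10 mm requirement, state it as a condition on the observed mean, and restate the power in 8.3 as at most about 50% at a true 10 mm. Add the true effect and SD at which it reaches 0.8. For illustration, at an assumed SD of 13.6 mm these effects are 12.8 mm (n = 17) and 11.6 mm (n = 50); the sponsor's own SD should replace that value.

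**Cost.** Wording in four sections, with no extra participants and no change to conduct. It should be settled before results are examined. Under the preferred option, a significant reduction below 10 mm would meet the primary endpoint. Under the alternative, the printed power becomes less favourable.

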# 8.2 Secondary Endpoints

Following the completion of both injections, volunteers will indicate which injection they preferred, with a no preference option included. Patients will also be queried on demographic information after the injections have been completed. They will be asked age, sex, role at University of Pennsylvania. Because pain is characterized as quantitative AND qualitative, include a free response section for comments, specifically asking Do you have any comments on how the kinetic anesthesia device affected your injection experience? A second qualitative entry section will ask: Were you bothered in any way by the VAD [check yes or no] if so please comment. Quantitative VAS data will be analyzed by a two-tailed ttest, and by linear regression model, incorporating location, and order of intervention (i.e. intervention first or second). Quantitative preferential data will be analyzed by logistic regression model incorporating location and order of intervention.

